ATTACHMENT 6: BARNES AKATHISIA RATING SCALE (BARS)

Instructions: Patient should be observed while they are seated, and then standing while engaged in neutral conversation (for a minimum of two minutes in each position). Symptoms observed in other situations, for example while engaged in activity on the ward, may also be rated. Subsequently, the subjective phenomena should be elicited by direct questioning.

Objective

- Normal, occasional fidgety movements of the limbs
- Presence of characteristic restless movements: shuffling or tramping movements of the legs/feet, or swinging of one leg while sitting, *and/or* rocking from foot to foot or "walking on the spot" when standing, but movements present for less than half the time observed
- 2 Observed phenomena, as described in (1) above, which are present for at least half the observation period
- Patient is constantly engaged in characteristic restless movements, *and/or* has the inability to remain seated or standing without walking or pacing, during the time observed

Subjective

Awareness of restlessness

- **0** Absence of inner restlessness
- 1 Non-specific sense of inner restlessness
- The patient is aware of an inability to keep the legs still, or a desire to move the legs, and/or complains of inner restlessness aggravated specifically by being required to stand still
- Awareness of intense compulsion to move most of the time *and/or* reports strong desire to walk or pace most of the time

Distress related to restlessness

- 0 No distress
- 1 Mild
- 2 Moderate
- **3** Severe

Global Clinical Assessment of Akathisia

- **Operation** Absent. No evidence of awareness of restlessness. Observation of characteristic movements of akathisia in the absence of a subjective report of inner restlessness or compulsive desire to move the legs should be classified as pseudoakathisia
- 1 Questionable. Non-specific inner tension and fidgety movements

- 2 *Mild akathisia*. Awareness of restlessness in the legs *and/or* inner restlessness worse when required to stand still. Fidgety movements present, but characteristic restless movements of akathisia not necessarily observed. Condition causes little or no distress.
- 3 *Moderate akathisia*. Awareness of restlessness as described for mild akathisia above, combined with characteristic restless movements such as rocking from foot to foot when standing. Patient finds the condition distressing
- 4 *Marked akathisia*. Subjective experience of restlessness includes a compulsive desire to walk or pace. However, the patient is able to remain seated for at least five minutes. The condition is obviously distressing.
- **Severe akathisia.** The patient reports a strong compulsion to pace up and down most of the time. Unable to sit or lie down for more than a few minutes. Constant restlessness which is associated with intense distress and insomnia.

Scoring the Barnes Akathisia Rating Scale

The Barnes Akathisia Rating Scale is scored as follows:

Objective Akathisia, Subjective Awareness of Restlessness and Subjective Distress Related to Restlessness are rated on a 4-point scale from 0-3 and are summed yielding a total score ranging from 0 to 9.

The Global Clinical Assessment of Akathisia uses a 5-point scale ranging from 0-4.

ATTACHMENT 7: COLUMBIA SUICIDE SEVERITY RATING SCALE (C-SSRS)

SUICIDAL IDEATION						
11 1 12 101 1 1. 100 1. 100 1. 100 101						
question 2 is "yes", ask questions 3, 4 and 5. If the answer to question 1 and/or 2 is "yes", complete			Lifetime: Time He/She Felt		Past Months	
"Intensity of Ideation" section below.	Most S	uicidal				
1. Wish to be Dead Subject and ages thoughts shout a wish to be dead or not alive anymore	a or wish to full salaan and not walso up	Yes	No	Yes	No	
Subject endorses thoughts about a wish to be dead or not alive anymore Have you wished you were dead or wished you could go to sleep and a						
	# Manual (1990)					
If yes, describe:						
 Non-Specific Active Suicidal Thoughts General non-specific thoughts of wanting to end one's life/commit suic 	ride (e.g., "I've thought about killing myself") without thoughts	Yes	No	Yes	No	
of ways to kill oneself/associated methods, intent, or plan during the as						
Have you actually had any thoughts of killing yourself?		_	_			
If yes, describe:						
3. Active Suicidal Ideation with Any Methods (Not Plan		Yes	No	Yes	No	
Subject endorses thoughts of suicide and has thought of at least one me specific plan with time, place or method details worked out (e.g. though	tht of method to kill self but not a specific plan). Includes person					
who would say, "I thought about taking an overdose but I never made	a specific plan as to when, where or how I would actually do					
itand I would never go through with it." Have you been thinking about how you might do this?						
If yes, describe:						
7 4 5 6 1 1 1 1 1 1 1 1 1 1 1 1 1 1 1 1 1 1	AC TE M					
 Active Suicidal Ideation with Some Intent to Act, with Active suicidal thoughts of killing oneself and subject reports having so 		Yes	No	Yes	No	
thoughts but I definitely will not do anything about them."	•					
Have you had these thoughts and had some intention of acting on the	em?		_	_	1.50	
If yes, describe:						
5. Active Suicidal Ideation with Specific Plan and Intent						
Thoughts of killing oneself with details of plan fully or partially worker. Have you started to work out or worked out the details of how to kill y		Yes	No	Yes	No	
NO. 10 100	voursety: Do you intena to carry out this plan:					
If yes, describe:						
INTENSITY OF IDEATION						
The following features should be rated with respect to the most the least severe and 5 being the most severe). Ask about time h						
the least severe and 5 being the most severe). Ask about time h	ersne was jeering the most suicidal.					
Lifetime - Most Severe Ideation: Type # (1-5)	Description of Ideation	1000	ost zere	Mo Sev		
200 KG 200 KG	Description of Incuron	Je,	rere	500	CIC	
Past X Months - Most Severe Ideation: Type # (1-5)	Description of Ideation					
Frequency						
How many times have you had these thoughts?						
(1) Less than once a week (2) Once a week (3) 2-5 times in w	reek (4) Daily or almost daily (5) Many times each day		-0	=		
Duration When you have the thoughts how long do they last?						
When you have the thoughts how long do they last? (1) Fleeting - few seconds or minutes	(4) 4-8 hours/most of day					
(2) Less than 1 hour/some of the time (5) More than 8 hours/persistent or continuous						
(3) 1-4 hours/a lot of time Controllability						
Could/can you stop thinking about killing yourself or wan	ting to die if you want to?					
(1) Easily able to control thoughts	(4) Can control thoughts with a lot of difficulty	9				
(2) Can control thoughts with little difficulty (3) Can control thoughts with some difficulty	(5) Unable to control thoughts (0) Does not attempt to control thoughts					
Deterrents	(0) Does not attempt to control thoughts					
Are there things - anyone or anything (e.g., family, religio	n, pain of death) - that stopped you from wanting to					
die or acting on thoughts of committing suicide?	W. F. F.					
 Deterrents definitely stopped you from attempting suicide Deterrents probably stopped you 	(4) Deterrents most likely did not stop you (5) Deterrents definitely did not stop you					
(3) Uncertain that deterrents stopped you	(0) Does not apply	_				
Reasons for Ideation	d. 4 d. 100 100 100 100 100 100 100 100 100 10					
What sort of reasons did you have for thinking about want or stop the way you were feeling (in other words you could						
feeling) or was it to get attention, revenge or a reaction fro						
(1) Completely to get attention, revenge or a reaction from others	(4) Mostly to end or stop the pain (you couldn't go on	32-	_	*	==	
(2) Mostly to get attention, revenge or a reaction from others (3) Equally to get attention, revenge or a reaction from others	living with the pain or how you were feeling) (5) Completely to end or stop the pain (you couldn't go on					
and to end/stop the pain	living with the pain or how you were feeling)					
a transfer from the state of th	(0) Does not apply					

© 2008 Research Foundation for Mental Hygiene, Inc

C-SSRS—Baseline/Screening (Version 1/14/09)

CHACID ALDER ATOD				D		
SUICIDAL BEHAVIOR (Check all that apply, so long as these are separate events; must ask about all types)			Lifetime		Past Years	
Actual Attempt: A potentially self-injurious act committed with at least some wish to die, as a result of act. Behavior was in part thought of as a conself. Intent does not have to be 100%. If there is any intent/desire to die associated with the act, then it can be considered a attempt. There does not have to be any injury or harm, just the potential for injury or harm. If person pulls trigger who mouth but gun is broken so no injury results, this is considered an attempt. Inferring Intent: Even if an individual denies intent/wish to die, it may be inferred clinically from the behavior or circumstance highly lethal act that is clearly not an accident so no other intent but suicide can be inferred (e.g., gunshot to head, jumping fror high floor/story). Also, if someone denies intent to die, but they thought that what they did could be lethal, intent may be inferred. Have you made a suicide attempt?	n actual suicide ile gun is in s. For example, a n window of a	Yes	No	Yes	No	
Have you done anything to harm yourself? Have you done anything dangerous where you could have died? What did you do? Did you as a way to end your life? Did you want to die (even a little) when you ? Were you trying to end your life when you ? Or Did you think it was possible you could have died from ? Or did you do it purely for other reasons / without ANY intention of killing yourself (like to relieve stress get sympathy, or get something else to happen)? (Self-Injurious Behavior without suicidal intent)	, feel better,		l # of empts	Total Atter	1# of mpts	
If yes, describe:		Yes	No	Yes	No	
Has subject engaged in Non-Suicidal Self-Injurious Behavior?						
Interrupted Attempt: When the person is interrupted (by an outside circumstance) from starting the potentially self-injurious act (if not for that, actual have occurred). Overdose: Person has pills in hand but is stopped from ingesting. Once they ingest any pills, this becomes an attempt rather than the properties of the properties o		Yes	No	Yes	No	
attempt. Shooting: Person has guis mand out a suppleat from ngesting. Once they ingest any pins, this sections an attempt attempt they pull the trigger, even if the gun fails to fire, it is an attempt. Jumping: Person is poised to jump, is grabbed and taken down Hanging: Person has noose around neek but has not yet started to hang - is stopped from doing so. Has there been a time when you started to do something to end your life but someone or something stopp you actually did anything? If yes, describe:	ng trigger. Once from ledge.	Tota	ıl # of rupted		l#of upted	
Aborted Attempt:		Yes	No	Yes	No	
When person begins to take steps toward making a suicide attempt, but stops themselves before they actually have engaged in any self-destructive behavior. Examples are similar to interrupted attempts, except that the individual stops him/herself, instead of being stopped by something else. Has there been a time when you started to do something to try to end your life but you stopped yourself before you actually did anything? If yes, describe:			200		□ l#of arted	
Dranauatom: Acts on Dahavion						
Preparatory Acts or Behavior: Acts or Behavior: Acts or preparation towards imminently making a suicide attempt. This can include anything beyond a verbalization or thought assembling a specific method (e.g., buying pills, purchasing a gun) or preparing for one's death by suicide (e.g., giving things a suicide note). Have you taken any steps towards making a suicide attempt or preparing to kill yourself (such as collecting).	way, writing a	Yes	No	Yes	No	
getting a gun, giving valuables away or writing a suicide note)? If yes, describe:	A PARTIE N					
Suicidal Behavior:		Yes	No	Yes	No	
Suicidal behavior was present during the assessment period?						
Answer for Actual Attempts Only	Most Recent Attempt Date:	Most Letl Attempt Date:		Initial/Fi Attempt Date:	rst	

This document describes the statistical methods and data presentations to be used in the summary and analysis of data from Protocol MIN-101C18. Background information is provided for the overall study design and objectives. The reader is referred to the study protocol and electronic case report forms (eCRFs) for details of study conduct and data collection.

1.1. STUDY OVERVIEW

This is a prospective, open-label, one-sequence, inpatient, clinical study of CYP2D6 normal metabolizer (NM) subjects with moderate to severe negative symptoms of schizophrenia. be coadministered to subjects already being administered roluperidone to determine its effect on the PD and PK of roluperidone. Eligible subjects will undergo 3 study phases as follows:

- Screening Phase: Between 2 and up to 28 days during which study eligibility will be established and subjects receiving psychotropics will be washed out. Discontinuation of psychotropics must occur at least 2 days prior to the start of Treatment Phase 1 (Day 1). Subjects will be admitted to the site on Day -2 and complete a Baseline Visit on Day -1.
- Treatment Phase 1: After the Baseline Visit (Day -1), roluperidone 64 mg/day will be administered as a monotherapy for 7 days (Days 1-7).
- Treatment Phase 2: Concomitant administration of olanzapine 10 mg/day and roluperidone 64 mg/day for 10 days, starting on Day 8 (Days 8-17). Subjects may be discharged from the clinic at least 48 hours after the last administration of the study drugs and after the collection of the last plasma sample; however, the inpatient period may be extended at the discretion of the investigator.

An End of Study (EOS) visit will take place at least 14 days after the last dose of study treatment. After the EOS visit, the medications and clinical care of the subject will be managed as per the judgement of the investigator/clinician.

Statistical Analysis Plan Final Version

1.2. STUDY MEASUREMENTS AND VISIT SCHEDULE

Phase	SCR	Admis- sion	BL		Tr	eatn	nent l	Phas	e 1						Tı	eatm	ent Pl	nase 2					EOS/ ET
Study Day	-28 to -3	-2	-1	1	2	3	4	5	6	7	8	9	10	11	12	13	14	15	16	17	18	19	31 (+2)
Informed consent	X																						
Inclusion & exclusion criteria	X		Xa																				
Demographics	X																						
Medical history/update	X		X																				
Physical examination	X		X																	X			X
Institutionalization			$\leftarrow \cdots$	• • •	• • •	• • •	• • •	• • •	• • •	• • •	• • • •	• • •	• • • •	• • • •	• • • •	• • •	• • • •	• • • •	• • • •	• • • •	\rightarrow		
Roluperidone administration				X	X	X	X	X	X	X	X	X	X	X	X	X	X	X	X	X			
Olanzapine administration											X	X	X	X	X	X	X	X	X	X			
Vital signs ^b	X		X	X	X	X	X	X	X	X	X	X	X	X	X	X	X	X	X	X	X	X	X
Weight	X		X							X										X			X
Height	X																						
Triplicate ECG ^c	X		X	X	X	X	X	X	X	X	X	X	X	X	X	X	X	X	X	X	X	X	X
CYP2D6 genotype	X ^d																						
Chemistry & hematology	X		X							X										X			X
Urinalysis ^e	X		X							X										X			X
Drug screen, alcohol test, and COVID-19	X		X																				
PK samplesf				X	X	X	X	X	X	X	X	X	X	X	X	X	X	X	X	X	X	X	
Serology	X																						
Serum pregnancy test	X		X																	X			X
FSH test	X																						
Tuberculosis test	X																						
MINI	X																						
C-SSRS	X		X	X						X	X									X			X
	X		X							X										X			X
CGI-S	X		X							X										X			X
BARS	X		X	Ì						X	X									X			X
AIMS	X		X							X	X									X			X
	X		X							X										X			X

Minerva Neurosciences, Inc.

MIN-101C18

Statistical Analysis Plan Final Version

Phase	SCR	Admis- sion	BL		Treatment Phase 1		Treatment Phase 2										EOS/ ET						
Study Day	-28 to -3	-2	-1	1	2	3	4	5	6	7	8	9	10	11	12	13	14	15	16	17	18	19	31 (+2)
Prior & Concomitant medications	X		←→							•													
Adverse events	X		←						•														

NOTE: There is no washout period between Treatment Phases.

Abbreviations: AIMS = abnormal Involuntary Movement Scale; BARS = Barnes Akathisia Rating Scale; BL = baseline; CGI-S = Clinical Global Impression – Severity C-SSRS = Columbia Suicide Severity Rating Scale; ECG = electrocardiogram; EOS = end-of-study; ET = early termination; PK = pharmacokinetics; SCR = screening; SCR = screening.

^a Verify eligibility.

^b Vital signs include blood pressure (standing and supine), pulse, oral/tympanic temperature, and respiratory rate. During Treatment Phase 1, vital signs are assessed prior to PK sampling at pre-dose and 6 hours post-dose on Days 1-7. During Treatment Phase 2, vital signs are assessed prior to PK sampling at pre-dose and 6 hours post-dose on Days 8-17 and 24 hours after last dose of study drug is administered (eg, Days 18 and 19).

^c Three sets of triplicate ECGs (1 minute apart within 5 minutes; total of 9 ECGs are recorded at Baseline (Day -1). Other ECG assessments are recorded in triplicate prior to PK sampling. During Treatment Phase 1, ECGs are recorded at pre-dose and 6 hours post-dose on Days 1-7. During Treatment Phase 2, ECGs are recorded pre-dose and 6 hours post-dose on Days 8-17 and 24 hours and 48 hours after last dose of study drug is administered (eg, Days 18 and 19).

^d CYP2D6 genotyping to be performed.

e Urinalysis will be performed by dipstick. Urine will be sent to the laboratory for microscopic analysis only in the event that the dipstick results are abnormal.

f After vital signs and triplicate ECG. During Treatment Phase 1, PK samples for roluperidone will be obtained at time 0 (pre-dose), 1, 2, 3, 4, 5, 6, 8, 10, 12, 14, 16, 18, and 24 hours post-dose on Days 1 and 7, at 6 hours post dose on Day 2, and at pre-dose and 6 hours post-dose on Days 3-6. During Treatment Phase 2, PK samples for roluperidone and olanzapine will be obtained at 6 hours post-dose on Day 8, time 0 (pre-dose) and 6 hours post-dose on Days 9-16, and starting on Day 17 at time 0 (pre-dose), 1, 2, 3, 4, 5, 6, 8, 10, 12, 14, 16, 18, 24, 28, 32, 36, and 48 hours post-dose. If a significant prolongation in QT is observed, a PK sample should be obtained.

MIN-101C18

Statistical Analysis Plan Final Version

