6.1.3. Baseline Visit

At the Baseline visit on Day -1, subjects will complete admission procedures and confirm eligibility for enrollment. Vital signs, electrocardiogram (3 sets of triplicate ECG), body weight, and height will be measured. Laboratory samples for hematology, clinical chemistry, and urinalysis (by dipstick) will be performed for all subjects. AIMS, CGI-S, BARS, and C-SSRS will also be administered.

6.1.4. Treatment Phase 1

In Treatment Phase 1, beginning on Day 1, subjects will receive 64 mg roluperidone each day at approximately the same time (between approximately 7:00 and 10:00 AM), followed by sequential collection of blood samples for measurement of plasma concentrations of roluperidone and ECG assessments, until Day 7. On Days 1 and 7, subjects will receive the study drug after fasting for at least 9 hours starting the night before. Subjects will receive standardized light meals approximately 2 hours after dosing. Vital signs, ECGs (in triplicate), and PK samples at specified time points will be collected throughout Treatment Phase 1. AIMS, CGI-S, BARS, C-SSRS will be administered on Day 7. Subjects will remain at the clinic after Day 7 to continue Treatment Phase 2.

6.1.5. Treatment Phase 2

In Treatment Phase 2, beginning on Day 8 subjects will receive study drugs (roluperidone and olanzapine) each day at approximately the same time followed by sequential collection of blood samples for measurement of plasma concentrations of both drugs and ECG assessments until Day 17. On Day 17, subjects will receive the study drug after fasting for at least 9 hours starting the night before. Subjects will receive standardized light meals approximately 2 hours after dosing. Vital signs, ECGs (in triplicate), and PK samples at specified time points will be collected throughout Treatment Phase 2. AIMS, BARS, and will be administered on Day 8, and AIMS, CGI-S, BARS, CC-SSRS will be administered on Day 17. Subjects may be released from the clinic after the collection of the last plasma sample (at least 48 hours after the last administration of the study drugs); however the inpatient period may be extended at the discretion of the investigator.

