3.2.5. Definitions and Terminology

Baseline Value

For quantitative safety measures, Baseline will be defined as the last valid evaluation completed before the study drug administration on Day 1. For ECG measures, including QTcF, Baseline will be defined as the mean of the triplicate set (total of 3 ECGs) performed pre-dose on Day 1 in Treatment Phase 1. This will also be referred to as Study Baseline.

A second Baseline will be used and will be referred to as the Treatment Phase 2 Baseline. For ECG, Treatment Phase 2 Baseline will be the mean of the triplicate ECGs (total of 3 ECGs) performed predose on Day 8.

Study Day

Study Day is defined relative to Day 1. Thus, the study day of an event occurring on or after Day 1 is calculated as:

Study Day = event date - date of Day 1 + 1.

The study day of an event occurring prior to Day 1 is calculated as:

Study Day = event date - date of Day 1.

Days on Study

Days on Study is calculated as Final Day on Study based on the EOS eCRF page – First Day on Study Drug + 1.

Treatment Phase Day

The study day within a treatment phase. Treatment Phase Day will be defined within each Treatment Phase 1 or 2.

Final Version

Treatment Phase Day = event date - date of Day 1 of Treatment Phase X + 1.

Study Time Point

Study Time Point is the nominal time point as recorded on the CRF.

Change from Baseline

Change from Baseline for a given endpoint is defined as the Study Time Point X value minus the Baseline Value. Change from Baseline may be study-specific (i.e., across all study phases), or Treatment Phase-specific (within any specific Treatment Phase). In the latter case, Baseline will be Treatment Phase specific.

Adverse Event

An adverse event is any untoward medical occurrence in a clinical study subject administered a medicinal (investigational or non-investigational) product. An adverse event does not necessarily have a causal relationship with the treatment. An adverse event can, therefore, be any unfavorable and unintended sign (including an abnormal finding), symptom, or disease temporally associated with the use of a medicinal (investigational or non-investigational) product, whether or not related to that medicinal (investigational or non-investigational) product.

This includes any occurrence that is new in onset or aggravated in severity or frequency from the Baseline condition, or abnormal results of diagnostic procedures, including laboratory test abnormalities.

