5.3.4. Other Safety Analyses

Descriptive summaries of vital signs and their respective change from Baseline values will be presented by time point and treatment group. The number and percentage of subjects with PCS vital signs occurring post-baseline will also be summarized by time point and treatment group. All abnormalities that occur post-baseline, regardless of Baseline status will be included. All vital signs will be listed with PCS vital signs flagged.

Table 3. Criteria For Potentially Clinically Significant Vital Signs

Vital Sign Parameter	Flag	Criteria
Systolic Blood Pressure	High	≥ 150 mmHg
(mmHg)	Low	≤ 80 mmHg
Diastolic Blood Pressure	High	≥100 mmHg
(mmHg)	Low	≤ 45 mmHg
Heart Rate (bpm)	High	> 115 bpm
	Low	< 45 bpm
Temperature (°C)	High	≥ 38 °C
	Low	< 35 °C

ECG parameters and their change from Baseline (using both Study Baseline and Treatment Phase 2 Baseline) will be summarized with descriptive statistics by time point and treatment group. ECG parameters will include heart rate, PR interval, RR interval, QRS interval, QT interval, and QTc interval corrected for heart rate using QTcB and QTcF. QTcF values will also be tabulated for their absolute values and tabulated relative to Baseline measurements in order to detect individual QTcF changes.

Additionally, the number and percentage of subjects with post-baseline QTcF interval > 450 - 480 milliseconds (msec), > 480 - 500 msec, or > 500 msec will be summarized, as will the number and percentage of subjects with QTcF interval increases from Baseline of > 30 - 60 msec or > 60 msec. For these summaries, worst-case assignments will be made to ensure subjects with such values are not counted more than once. For example, a subject with QTc interval > 500 msec will count once in the > 500 msec category and will not appear in the > 450 - 480 or > 480 - 500 msec categories. Similar conventions will be used for the > 30 - 60 and > 60 msec categories.

All ECG assessments and abnormalities in ECG waveform that are changes from Baseline readings will also be reported in a listing.

Final Version

Table 4. Potentially Clinically Significant Criteria for ECG

[figure not shown]
Variable	Units	PCS Criteria Low Values	PCS Criteria High Values	Change from Baseline or Observed Value
Heart Rate	beats/min	<45	>115	-
QTcF Interval	msec	-	>450 Males >470 Females	>30-60, > 60, > 450-480, > 480-500, > 500
QRS Interval	msec	-	>120	-
PR Interval	msec	-	>220	-

All physical examination results will be listed.

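### The 6-hour QTcF change from Study Baseline cannot be separated from any morning-to-afternoon or meal shift, because the Day -1 ECGs have no set clock or meal times

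*SAP*

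**What the plan says.** - **Day -1 ECGs.** Footnote c of the schedule in SAP 1.2, matched by footnote c in the protocol schedule, reads: "Three sets of triplicate ECGs (1 minute apart within 5 minutes; total of 9 ECGs are recorded at Baseline (Day -1". Protocol 6.1.3 repeats the requirement: "electrocardiogram (3 sets of triplicate ECG), body weight, and height will be measured". Only the spacing inside a triplicate is given. Nothing fixes the hour, the interval between sets or the relation to meals.
- **Study Baseline.** For QTcF, SAP 3.2.5 states: "Baseline will be defined as the mean of the triplicate set (total of 3 ECGs) performed pre-dose on Day 1 in Treatment Phase 1". The nine Day -1 tracings do not enter it.
- **Second baseline.** The same section adds: "Treatment Phase 2 Baseline will be the mean of the triplicate ECGs (total of 3 ECGs) performed predose on Day 8". By then seven roluperidone doses have been given.
- **Dosing and meals.** Protocol 6.1.4 puts the dose "between approximately 7:00 and 10:00 AM". It also says: "On Days 1 and 7, subjects will receive the study drug after fasting for at least 9 hours starting the night before". On food: "Subjects will receive standardized light meals approximately 2 hours after dosing".
- **On-treatment ECGs.** Triplicates are taken pre-dose and 6 hours post-dose on Days 1 to 17, then on Days 18 and 19.
- **Analysis.** SAP 5.3.4 states: "ECG parameters and their change from Baseline (using both Study Baseline and Treatment Phase 2 Baseline) will be summarized". The summaries are descriptive, by time point and treatment group. Subjects with QTcF increases of >30-60 and >60 msec are also counted. No clock matching or diurnal adjustment is planned, and SAP 3.2 describes an open-label, one-sequence study.

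**The concern.** ECG is listed under the primary objective in SAP 2, and Protocol 1.2 names QT prolongation as a roluperidone risk. The 6-hour readings are the only scheduled post-dose ECGs before 24 hours.

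The Study Baseline and the 6-hour reading differ in three ways: drug exposure, hour of the day and time since food. Only the first is of interest. If QTcF moves between a fasting morning and a fed afternoon without study drug, the 6-hour rows report that movement as part of the drug effect. An upward shift would overstate the effect and a downward one could hide it. Enrolling more subjects would not reduce it.

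The plan already collects nine Day -1 tracings that could measure the shift, but places none of them at the relevant hour.

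**Working it through.** The plan has no figure for ECG precision or variability. Its only precision statement (SAP 3.1) concerns pharmacokinetic ratios and plays no part here.

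**1. Clock and meal positions (Protocol 6.1.4).**
- Study Baseline: about 07:00-10:00, fasted at least 9 hours.
- 6-hour ECG: 07:00 + 6 h = 13:00 to 10:00 + 6 h = 16:00.
- Time since the light meal: 6 - 2 = about 4 hours.

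**2. Time points affected (schedule footnotes).**
- 6-hour readings: 7 (Days 1-7) + 10 (Days 8-17) = 17.
- Pre-dose readings after the baseline: Days 2-17 = 16.
- After the last dose: Days 18 and 19 = 2.
- Share affected through Day 19: 17/(17 + 16 + 2) = 17/35 = 49%.

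The other 18 fall at about the baseline hour. Their meal state is less certain, because fasting is specified only for Days 1, 7 and 17.

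**3. What the 6-hour change estimates.** Let e be the drug effect at 6 hours and s the off-drug shift from fasting morning to fed afternoon.
- 6-hour reading minus Study Baseline = e + s.
- 6-hour reading minus an off-drug reading at the same hour and meal state = e.
- Phase 2 minus Phase 1, both at 6 hours = (e2 + s) - (e1 + s) = e2 - e1.

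No ECG free of study drug is tied to the 6-hour clock time, so s cannot be estimated from the planned data. In the third line, an additive s cancels.

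**4. Scale under assumptions.** The documents give neither s nor the SD of a QTcF change. Assume s from -10 to +10 msec and SD 10 to 15 msec.

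The 90% half-width of a mean change is t(0.95, n-1) × SD/√n:
- n = 12: 5.2 msec (SD 10) to 7.8 msec (SD 15).
- n = 18: 4.1 to 6.2 msec.

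For an assumed true effect of 10 msec, P(change >30) = 1 - Φ((30 - 10 - s)/SD) at one 6-hour reading:

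| s (msec) | Mean change shown | Share >30, SD 10 | Share >30, SD 15 | Subjects of 12, SD 15 |
|---|---|---|---|---|
| -10 | 0 | 0.1% | 2.3% | 0.3 |
| -5 | 5 | 0.6% | 4.8% | 0.6 |
| 0 | 10 | 2.3% | 9.1% | 1.1 |
| +5 | 15 | 6.7% | 15.9% | 1.9 |
| +10 | 20 | 15.9% | 25.2% | 3.0 |

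For >60 msec at SD 15, the same formula gives 1 - Φ(50/15) = 0.04% at s = 0 and 1 - Φ(40/15) = 0.4% at s = +10. That category hardly moves.

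These are shares at a single reading. SAP 5.3.4 counts each subject once, by worst case over all readings, so the table shows direction and scale and does not predict the SAP's counts.

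**The case against.** **Nothing shows that a shift exists.** Correct. The shift, the SD and the true effect in the illustration are all assumed. A reader might infer that the QTcF results are biased. The documents do not support that; they show only that the 6-hour design cannot tell drug effect from shift.

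**The added effect of olanzapine is still estimable.** This stands. A reader might infer that the co-administration question is compromised as a whole. It is not: doses are given at about the same time each day (Protocol 5.2), and an additive shift cancels between phases at 6 hours. Days 7 and 17 are the best-matched pair, since fasting is specified for both. The SAP tabulates these rows but defines no such contrast, and the contrast cannot recover the roluperidone-alone change or the total change from Study Baseline.

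**Absolute categories are safe.** Agreed. The >450-480, >480-500 and >500 msec counts use no baseline.

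**The Treatment Phase 2 Baseline covers it.** It does not. That is also a pre-dose morning reading, and it is taken on roluperidone.

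**Day -1 is not a clean reference.** This stands in part. Protocol 3.1 requires psychotropics to stop at least 2 days before Day 1, Protocol 6.1.1 says by Day -2, and inclusion criterion 9 says by Baseline. Day -1 is therefore free of study drug but may follow withdrawal by only about a day, and Attachment 1 lists many antipsychotics as QT-prolonging. Replacing the 6-hour baseline outright could exchange a clock shift for carry-over. That argues for an added analysis rather than a replacement.

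**Conclusion.** The point holds within limits. At 17 time points, the QTcF change from Study Baseline, and what those readings contribute to the >30-60 and >60 msec counts, combine drug effect with any off-drug time-of-day and meal shift. The quantities affected are the roluperidone-alone change and the total change from Study Baseline at 6 hours.

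The bias equals the shift, whose size and sign the documents do not give. A shift of 5 msec would be about equal to, or below, the 90% half-width for 12 subjects, and one of 10 msec would exceed it, at the assumed SDs of 10 to 15 msec. The clock times rest on the dosing window in Protocol 6.1.4. The meal part assumes that its meal timing applies on each dosing day, and the text is explicit about fasting only on Days 1, 7 and 17. The clock mismatch holds on all 17 days.

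This is a worthwhile, inexpensive improvement to a safety measure under the primary objective. It does not invalidate the planned ECG analysis.

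**What to change.** **Schedule.** Keep the nine Day -1 ECGs. In Protocol 6.1.3 and in footnote c of both documents, place at least one set at the subject's planned dosing clock time and at least one at the clock time 6 hours later. Use the Day 1 meal timing and record the actual times.

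**Analysis (SAP 3.2.5 and 5.3.4).**
- Keep the Day 1 pre-dose Study Baseline and the tables built on it.
- Add a clock-matched change for the 6-hour rows, using the Day -1 set or sets at that hour, and repeat the >30-60 and >60 msec counts on that basis.
- Add the within-subject Day 17 versus Day 7 contrast at 6 hours.
- If Day -1 ECGs are already recorded, use sets within about 1 hour of the 6-hour clock time and flag subjects without one.
- State as a limitation that Day -1 readings may carry residual effect of recently stopped psychotropics.

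**Reconcile.** The protocol attaches the term Baseline to the Day -1 visit and uses it in the QTcF-change stopping criterion (Protocol 7.2), while SAP 3.2.5 defines it as Day 1 pre-dose. The passages must be brought into agreement on which reading is meant.

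**Cost.** No extra ECG, visit or staff. A protocol amendment with IRB approval is needed (Protocol 13.1), sites must space the Day -1 sets in subjects who are already inpatients, and the report carries a second set of 6-hour ECG rows.
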